7.8.2 Disposition of Subjects

A summary of the number of subjects enrolled, the number of subjects treated (with at least one dose of study medication afatinib) and the number and percentage of subjects withdrawing from the study will be provided. Subjects withdrawing from study will also be summarized by major reason. (Analysis set: ES).

7.9 EXPOSURE TIME

See [Section 7.6](#), [Section 7.7.1](#) and [Section 7.8](#).

7.10 SAFETY ANALYSIS

All the safety analysis will be performed on Treated Set (TS).

7.10.1 Adverse events

All AEs will be collected and documented on the eCRF from the day of signing informed consent up to 30 days after the last dose of afatinib administration. In addition, all ADRs associated with afatinib and AEs with fatal outcome must be collected and documented on the eCRF after the end of residual effect period (30 days after the last dose of afatinib administration) up to the end of study.

Adverse events will be coded using the Medical Dictionary for Regulatory Activities (MedDRA) Version 22.1 or higher.

Treatment-emergent adverse events will be tabulated and are defined as those adverse events that start on or after the date/time of first dose of Afatinib until 30 days after last dose of Afatinib, all AEs related to Afatinib after 30 days from last dose of Afatinib will be analysed as treatment-emergent AEs.

Where dates are missing or partially missing, adverse events will be assumed to be treatment-emergent, unless there is clear evidence (through comparison of partial dates) to suggest that the adverse event started prior to the first dose of study treatment.

For the purpose of calculating treatment emergent AEs, incomplete onset dates will be imputed as below:

If onset date is completely missing, onset date is set to the date of first dose of trial medication.

If (year is present and month and day are missing) or (year and day are present and month is missing):

- If year = year of first dosing, then set month and day to month and day of first dosing
- If year < year of first dosing, then set month and day to December 31.
- If year > year of first dosing, then set month and day to January 1.

If month and year are present and day is missing:

- If year=year of first dosing and
 - If month = month of first dose then set day to day of first dose
 - If month < month of first dose then set day to last day of month
 - If month > month of first dose then set day to first day of month

Proprietary confidential information © 2024 Boehringer Ingelheim International GmbH or one or more of its affiliated companies

- If year < year of first dose then set day to last day of month
- If year > year of first dose then set day to first day of month

For all other cases, set onset date to date of first dosing.

Adverse event summaries will be ordered in terms of decreasing frequency for SOC, and PT within SOC, and then alphabetically for SOC, and PT within SOC.

ADRs are defined as TEAEs related to study treatment Afatinib, missing causality will be assumed as related to Afatinib.

The AE severity are assessed by intensity graded according to United States (US) national cancer institute's (NCI) (CTCAE Version 5.0), for each subject and each adverse event, the worst severity (CTCAE Grade) recorded will be attributed and used in the by-severity summaries. If severity is missing, the worst case will be assumed.

The Following summaries will be provided:

- An overview of any AEs, TEAEs, ADRs, serious TEAEs, serious ADRs, and TEAEs leading to withdrawals, all AEs leading to death, and TEAEs leading to death will be presented.
- A summary of the number and percentage of subjects reporting a treatment-emergent adverse event by SOC, and PT
- A summary of the most common treatment-emergent adverse events by SOC, and PT (> 5% will be reported).
- A summary of the number and percentage of subjects reporting a serious treatment-emergent adverse event by SOC and PT.
- A summary of the number and percentage of subjects reporting a drug related treatment-emergent adverse event (ADR) by SOC and PT
- A summary of the number and percentage of subjects reporting a drug related serious TEAEs by SOC and PT
- A summary of the number and percentage of AEs leading to death during the study by SOC and PT.
- A summary of the number and percentage of TEAEs leading to death during the study by SOC and PT.
- A summary of the number and percentage of subjects with TEAEs leading to discontinuation of study treatment by SOC and PT.
- A summary of the number and percentage of subjects reporting a treatment-emergent adverse event by CTCAE Grade, SOC and PT

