9.7.3 Safety Analysis

All adverse events and adverse drug reactions collected per study protocol will be included and summarised in the interim safety analysis and in the final study report.

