11.2 ADVERSE EVENT AND SERIOUS ADVERSE EVENT COLLECTION AND REPORTING

The investigator shall maintain and keep detailed records of all AEs in their patient files.

Collection of AEs

The study design is of non-interventional nature, and the study is conducted within the conditions of the approved marketing authorisation. Sufficient data from controlled interventional trials are available to support the evidence on the safety and efficacy of the afatinib. For this reason, the following AE collection and reporting requirements have been defined.

The following must be collected by the investigator in the eCRF from signing the informed consent onwards until the end of the study:

- From signing the informed consent onwards until 30 days after the last dose of afatinib administration:
 - *All AEs (serious and non-serious)
- From the end of the residual effect period (30 days after the last dose of afatinib administration) onwards until the individual patient's end of study:
 - All ADRs (serious and non-serious) associated with afatinib
 - *All AEs with fatal outcome

*Exemption regarding progression of underlying malignancy:

“Progressive Disease (PD) of the malignancy” is the study endpoint and will be recorded on the appropriate page of the eCRF.

During the whole study, progression of the malignancy under study (including signs and symptoms of progression) should not be reported as adverse event unless the progression is considered related to afatinib.

When there is evidence suggesting a causal relationship between afatinib and the progression of the underlying malignancy, the event must be reported as an AE on the eCRF and on the NIS AE Form.

All AEs that are to be collected including those persisting after study completion, must be followed up until they are resolved, have been sufficiently characterised, or no further information can be obtained.

Causal relationship of adverse event

The definition of an adverse reaction implies at least a reasonable possibility of a causal relationship between a suspected medicinal product and an AE. An adverse reaction, in contrast to an AE, is characterised by the fact that a causal relationship between a medicinal product and an occurrence is suspected.

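### SAP 7.10.1 classifies TEAEs by start date alone and nests ADRs inside them, so an AE that starts between consent and first dose and worsens on afatinib can drop out of the TEAE and ADR tables

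*SAP*

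**What the plan says.** AE collection starts before treatment. Protocol 11.2 requires all AEs to be recorded "From signing the informed consent onwards until 30 days after the last dose of afatinib administration". Protocol 9.1 sets consent at Day 0 and first dose at Day 1.

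SAP 7.10.1 then sets the analysis rules:

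- TEAEs are "defined as those adverse events that start on or after the date/time of first dose of Afatinib". The window closes 30 days after the last dose.
- The one extension looks forward: "all AEs related to Afatinib after 30 days from last dose of Afatinib will be analysed as treatment-emergent AEs".
- An AE with a missing or partial date is treatment-emergent by default: "unless there is clear evidence (through comparison of partial dates) to suggest that the adverse event started prior to the first dose of study treatment".
- "ADRs are defined as TEAEs related to study treatment Afatinib". Missing causality counts as related.
- For each patient and event, "the worst severity (CTCAE Grade) recorded will be attributed and used in the by-severity summaries".

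The protocol puts no onset condition on ADRs. Section 9.3.2.2 lists them as afatinib-related AEs, and section 11.1 defines an adverse reaction by a reasonable possibility of causation. On scope, section 9.7.3 says: "All adverse events and adverse drug reactions collected per study protocol will be included and summarised". SAP section 4 declares no change to the planned analysis.

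**The concern.** A definition that looks only at the start date cannot see worsening. An AE that is mild before the first dose and becomes severe, serious and drug-related on treatment is still one record with a pre-dose start. It fails the TEAE rule. Because ADRs are defined inside TEAEs, it fails the ADR rule as well, whatever the investigator's causality assessment.

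Safety is a secondary outcome, and the protocol describes it by incidence, seriousness and intensity. At stake is whether the SAP tables report the ADRs that the protocol promises. The SAP narrows the protocol's ADR definition without declaring it. In rows with small counts, such as serious ADRs or discontinuations, a single missing patient would be visible.

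**Working it through.** The plan states no figure on this point, so the check is to trace one event through the rules.

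**Test case.** An AE starts on Day 0 at grade 1 with a fully known date. On treatment it reaches grade 3, becomes serious and is assessed as related to afatinib. The site keeps it under one record.

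1. *Is it collected?* Yes. Protocol 11.2 and SAP 7.10.1 both collect from consent.
2. *Is it a TEAE?* No. It starts before the first dose. The late-event extension covers only related AEs beyond 30 days after the last dose. The missing-date default does not apply to a known date.
3. *Is it an ADR?* Not under the SAP, because it is not a TEAE. Under protocol 9.3.2.2 and 11.1 it is, because it is related.
4. *Does the worst-grade rule rescue it?* No. That rule gives the record grade 3, but the table by CTCAE grade is restricted to TEAEs.
5. *Does either document give a worsening its own onset date or require a new record?* No such text was found in the SAP or the protocol.

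**Where the event appears in the planned outputs** (SAP 7, 7.10.1 and 7.10.2):

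| Output | Test case included? |
|---|---|
| TEAEs by SOC and PT; most common TEAEs (> 5%) | No |
| Serious TEAEs | No |
| ADRs; serious ADRs | No |
| TEAEs leading to discontinuation | No |
| TEAEs by CTCAE grade | No |
| TEAEs leading to death | No |
| Overview, count of any AEs | Yes |
| All AEs leading to death (overview and SOC/PT table) | Yes, if fatal |
| Worst laboratory shift from baseline | Yes, if a laboratory change |
| Listings | Yes |

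The outputs that retain the event do not give ADR incidence or ADR grade.

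**Size.** Inputs: N = 76 (protocol 9.5), assuming that all 76 are in the Treated Set. The documents give no number k of affected patients, so k is an assumption.

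- Loss in an incidence = k/76.
- k = 0: 0 points.
- k = 1: 1/76 = 1.3 points.
- k = 4: 4/76 = 5.3 points.
- Entry to the > 5% table: 0.05 × 76 = 3.8, so 4 patients are needed (4/76 = 5.3%; 3/76 = 3.9%). One omitted patient can take a preferred term off that table if its true count is exactly 4.

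With a nominal window of one day, and with worsening also required, the low end of the range, including zero, is the more plausible.

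**The case against.** The strongest objection is that the loss is conditional. It occurs only if the worsening stays under the pre-dose record. The eCRF and its completion guidelines are cited but were not available for this review. If they require a new record at worsening, the new record starts on treatment and the existing rule captures it. This stands as a limit on the point. It does not remove it, because neither document states such a convention.

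Second, a reader might infer that every patient with symptoms before treatment is affected. The documents do not support that. AEs are collected only from consent, and earlier conditions are taken at baseline as medical history or comorbidities. Worsening of one of those on treatment would need its own AE entry with an on-treatment start, and that entry would be counted. Only AEs that start between consent and first dose are exposed.

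Third, a reader might infer that ADR incidence overall must be understated. For an event with a known date, the rule can only remove it. Other SAP rules push the other way, however: missing dates default to treatment-emergent, a missing day in the month of first dose becomes the first-dose date, missing causality counts as related and missing severity as worst. The net direction is not established.

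Fourth, protocol 11.2 (Table 4) requires serious ADRs to be reported within 24 hours with no onset condition, so a reader might see a required match between the safety database and the study tables. Neither document requires one. The mismatch that matters is between the SAP and the protocol on what an ADR is.

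**Conclusion.** The point holds as a definition problem of small expected size. By its own wording, SAP 7.10.1 leaves out of its TEAE and ADR tables an AE that starts between consent and first dose and worsens on afatinib under its original record. It does so even when the AE is judged related. That is narrower than protocol 9.3.2.2, 9.7.3 and 11.1.

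The event is not lost from the report altogether. It stays in the overview count of any AEs and in the listings, in the all-AEs-leading-to-death summaries if fatal, and in the laboratory shift table if it is a laboratory change.

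The conclusion rests on three assumptions: worsening is not entered as a new record, the onset date is known, and all 76 patients are treated (for the 1.3 points per patient). The number affected is unknown and may be zero. The documents do not support a claim of material or systematic understatement of toxicity. The correction is worth making because it is cheap and brings the SAP back into line with the protocol.

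**What to change.** Amend SAP 7.10.1 as follows:

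1. Extend the TEAE definition to AEs that start before the first dose and then worsen in CTCAE grade, or become serious, on or after the first dose and up to 30 days after the last dose. Also include any AE with pre-dose onset that the investigator explicitly assesses as related to afatinib. Keep the existing extension for late related AEs.
2. Keep ADRs as related TEAEs, now under this wider definition. Dropping the timing condition altogether would be a mistake: combined with the rule that missing causality counts as related, it could turn a pre-dose AE with a blank causality field into an ADR.
3. Apply that missing-causality rule only to AEs that start or worsen on or after the first dose.
4. For AEs with pre-dose onset, tabulate the worst grade on or after the first dose where dated grades exist, and otherwise the worst recorded grade.

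The cost is SAP wording and a small programming change. The downside is that a few more events count as treatment-emergent, and where grades are undated a pre-dose grade may be tabulated. A new instruction to sites is best avoided: the last patient was due in by December 2021, so it would mean retrospective queries. If the eCRF guideline already requires a new record at worsening, the SAP should say so.

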Medical judgment should be used to determine the relationship, considering all relevant factors, including the pattern of reaction, temporal relationship, de-challenge or re-challenge, confounding factors such as concomitant medication, concomitant diseases, and relevant history.

Arguments that may suggest a **reasonable causal relationship** could be:

- The event is **consistent with the known pharmacology** of the drug
- The event is known to be caused by or **attributed to the drug class**
- **A plausible time to onset of the event** relative to the time of drug exposure
- Evidence that the **event is reproducible** when the drug is re-introduced
- **No medically sound alternative etiologies** that could explain the event (e.g., pre-existing or concomitant diseases, or co-medications)
- The event is typically **drug-related and infrequent in the general population** not exposed to drugs (e.g., Stevens-Johnson syndrome)
- An indication of dose-response (i.e., greater effect size if the dose is increased, smaller effect size if the dose is diminished)

Arguments that may suggest that there is **no reasonable possibility of a causal relationship** could be:

- No plausible time to onset of the event relative to the time of drug exposure is evident (e.g., pre-treatment cases, diagnosis of cancer or chronic disease within days/weeks of drug administration; an allergic reaction weeks after discontinuation of the drug concerned)
- Continuation of the event despite the withdrawal of the medication, taking into account the pharmacological properties of the compound (e.g., after 5 half-lives). Of note, this criterion may not apply to events whose time course is prolonged despite removing the original trigger.
- Additional arguments amongst those stated before, like alternative explanation (e.g., situations where other drugs or underlying diseases appear to provide a more likely explanation for the observed event than the drug concerned).
- Disappearance of the event even though the study drug treatment continues or remains unchanged.

Intensity of adverse event

The intensity of AEs should be classified and recorded according to the CTCAE criteria in the eCRF.

Pregnancy:

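### SAP 7.10.1 imputes a missing AE grade as the worst case without capping it or tying it to outcome, so a non-fatal event could be counted in the fatal CTCAE grade

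*SAP*

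**What the plan says.** Protocol 11.2 asks the investigator to grade every event: "The intensity of AEs should be classified and recorded according to the CTCAE criteria in the eCRF". It gives no rule for a grade that is absent.

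SAP 7.10.1 adopts the same scale, in version 5.0. For each subject and each event, "the worst severity (CTCAE Grade) recorded will be attributed and used in the by-severity summaries". The next sentence is the imputation rule: "If severity is missing, the worst case will be assumed". No grade is named and there is no exception by outcome.

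The grade feeds one listed output: "A summary of the number and percentage of subjects reporting a treatment-emergent adverse event by CTCAE Grade, SOC and PT". Fatal events have their own outputs. The overview says "all AEs leading to death, and TEAEs leading to death will be presented", and a later item is "A summary of the number and percentage of TEAEs leading to death during the study by SOC and PT". Serious TEAEs also have their own table. None of these is described as derived from grade.

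Two general rules bear on the point. SAP 6.6 leaves other missing data as missing or unknown unless a rule elsewhere says otherwise. The introduction to SAP 7 shows a missing category in categorical tables whenever values are in fact missing.

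**The concern.** Worst-case imputation is a familiar safety convention. It works on a scale such as mild, moderate and severe, where the top category is still a judgement about intensity. The top category of CTCAE is a fact about outcome: Grade 5 is death. Imputing it for an event that the patient survived contradicts something already known about that patient.

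What is at stake is the credibility of one safety table in a small, descriptive, single-arm study. AE intensity is part of a named secondary outcome (Protocol 9.3.2.2, SAP 5.2), and this table is where it is reported. Protocol 11.2 exempts progression of the malignancy from AE reporting unless it is thought related to afatinib. True Grade 5 events should therefore be fewer than deaths, and even one or two imputed ones would stand out in that row.

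**Working it through.** The plan states no figure on this point, so there is nothing to reproduce. The check sets the rules side by side and then bounds the size.

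**Step 1. Is the term limited anywhere?** Neither document defines the worst case, caps the imputed grade below the fatal one, or refers to outcome when imputing a grade. SAP 6.6 does not help, because its default gives way to any rule stated elsewhere and SAP 7.10.1 states one. The protocol has no competing rule.

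**Step 2. What does the literal rule do?** Take a TEAE that is non-serious, resolved, and has no grade after data cleaning.

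| Output in SAP 7.10.1 | Driven by | Where this event falls |
|---|---|---|
| TEAEs by CTCAE grade, SOC and PT | Grade, imputed if missing | Top of the scale, Grade 5 |
| TEAEs leading to death | Not described as grade-derived | Not counted |
| Serious TEAEs | Seriousness | Not counted |

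Protocol 11.1 makes any event that results in death serious. The same event would thus be fatal in the first table and neither fatal nor serious in the other two.

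**Step 3. Size.** Inputs: 76 planned patients (Protocol 9.5), and the assumption that all of them are in the Treated Set. A subject counts once in a given row, so one affected subject with no true Grade 5 event adds at most

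1/76 = 0.013, or 1.3 percentage points,

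to the any-event Grade 5 count, if such a row is shown. For k affected subjects the ceiling is k/76. As an illustration only, k = 3 gives 3/76 = 3.9 points. A subject who already has a true Grade 5 event adds nothing to that count. The documents do not give k.

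**Limit of the check.** Neither document prints the CTCAE grade definitions. That Grade 5 means death comes from the scale the SAP names.

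**The case against.** The strongest reply is that the SAP never writes Grade 5. The rule follows directly on a sentence about the worst grade recorded for a subject and event, so a programmer might take it to mean the worst non-fatal grade, or the worst grade recorded for that subject. This stands in part. A reader should not infer that the sponsor has declared Grade 5 as the imputed value. But SAP 3 presents the document as outlining the programming specifications for the tables. A rule that allows several different tables, one of them plainly wrong, is not fit for that use.

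Second, missing grades should be rare. Intensity is a field the investigator must complete. Completeness checks run at entry (Protocol 9.8), and queries are raised and followed up (Protocol 9.6.2). Protocol 9.3 does warn that study variables may be unavailable under routine care, but a grade the investigator assigns is less exposed to that than a routine-care test. This stands, and it keeps the point minor.

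Third, the rule matches the SAP's other cautious choices, such as treating missing causality as related. That explains the intent, but those choices do not override a recorded fact. Imputing a fatal grade for a survivor does.

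Three stronger readings are tempting and are not supported:

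- **That reported deaths would be inflated.** The death summaries are separate and are not described as using grade, so they need not change. The raw eCRF data are also listed (SAP 7), which would expose the conflict.
- **That the incidence of Grade 3 or higher events would be inflated.** SAP 7.10.1 plans no such summary.
- **That an imputed grade becomes the patient's worst grade across all events.** Attribution is per subject and per event.

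**Conclusion.** The point holds as a minor error in a stated rule. Taken at its word, SAP 7.10.1 places an ungraded, non-fatal TEAE in the fatal grade of the by-grade table and sets that table against two others in the same section. The defect is more than a missing detail, because the literal reading gives a wrong result and nothing in either document blocks it.

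The effect is at most 1.3 percentage points per affected patient on the any-event Grade 5 count. This assumes 76 treated patients and the usual meaning of Grade 5 on the named scale. The total effect depends on a number of missing grades that the documents do not give and that is probably small. Time on treatment, overall survival and response rate are untouched. The documents do not support calling this a plan to report false deaths: they support saying that the rule, as worded, permits a wrong Grade 5 entry.

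**What to change.** Replace the sentence in SAP 7.10.1 with:

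> AEs whose CTCAE grade is still missing after query are shown in a Missing category in the by-grade summary; Grade 5 is assigned only when the recorded outcome of the AE is fatal.

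The Missing category is already allowed by the display rule at the start of SAP 7. Fatal outcome is already collected, since Protocol 11.2 requires AEs with fatal outcome to be documented in the eCRF. No substitute grade such as Grade 3 is needed: no planned summary would use it, and nothing in the documents supports that choice.

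The cost is one SAP sentence and the matching line of table programming, with no new data or site work. The one downside is that ungraded events no longer count towards a high grade, so the by-grade table is slightly less conservative for them. The Missing count shows the reader how many such events there are.
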